#### 4.4 Part 2: Dose Expansion

Upon identification of the Recommended Phase 2 Dose of itacitinib, an expansion cohort will open to the enrollment of 40 additional patients for further assessment of regimen safety and

efficacy. Enrollment will be conducted in two stages separated by an interim analysis. In the first stage of the dose-expansion study, 16 patients will be accrued. Of those 16 patients, 6 patients treated at the RP2D will be carried over from Part 1. In recognition of a potential accrual pause of at least 24 weeks if all 16 patients are required to complete six months of combination therapy, we will permit enrollment of an additional 3 patients after the first 10 eligible patients in the first stage of the dose-expansion study are enrolled if no more than 5 of 16 patients have experienced treatment failure (i.e., the addition of secondary systemic therapy or disease relapse or death) by the end of week 12 of treatment.

Once all 10 patients in Part 2 and the six patients treated at the RP2D in Part 1 have met treatment failure criteria or completed six months of combination therapy, whichever comes first, an interim analysis will be conducted to assess treatment efficacy. If  $\leq 7$  responses (CR or PR) in the first 16 enrolled patients are reported, the study will be stopped. Otherwise, the next stage of the expansion cohort will open to the enrollment of 30 additional patients.

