## 12 STATISTICAL CONSIDERATIONS

### 12.1 Sample Size Determination

#### Part 1

Part 1 has a maximum of 18 patients. Part 1 has a 3+3 dose de-escalation design with 3 doses and a maximum of 6 patients per dose.

#### Part 2

The sample size for Part 2 is 16-46 patients with 6 patients carried over from Part 1 at the RP2D. Simon’s optimal two-stage design will be used in Part 2. The primary outcome is the overall response rate (CR + PR) at 24 weeks. Withdrawal or progression prior to 24 weeks or missing 24-week assessment will be considered non-response. After the first 16 patients treated at the RP2D complete 24 weeks of therapy or meet treatment discontinuation criteria, enrollment will be put on hold and an interim analysis will be conducted. This study treatment will be considered promising if the overall response rate at 24 weeks is  $\geq 60\%$  and unacceptable if the overall response rate at 24 weeks is  $\leq 40\%$ . 50% is the reported best overall response rate of current first-line therapy with high-dose steroids. The null hypothesis that the true response rate is  $\leq 40\%$  will be tested against a one-sided alternative.

In the first stage of the dose-expansion study, 16 patients will be accrued and followed through the first 24 weeks of treatment. Of those 16 patients, 6 patients will be carried over from Part 1 at the RP2D. In recognition of a potential accrual pause of at least 24 weeks if all 16 patients are required to complete six months of combination therapy, we will permit enrollment of an additional 3 patients (20%) after the first 10 eligible patients in the first stage of the dose-expansion study are enrolled if no more than 5 of 16 patients have experienced treatment failure (i.e. addition of secondary systemic therapy or disease relapse or death) by the end of week 12 of treatment. If there are 7 or fewer responses in the first 16 patients enrolled, the study will be stopped. Otherwise, 30 additional patients

will be accrued for a total of 46. The null hypothesis will be rejected if 24 or more responses are observed in 46 patients. This design yields a type I error rate of 0.0486 and a power of 80% when the true response rate is  $\geq 60\%$ .

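### The rule for early enrolment during stage 1 does not count all the events that decide stage 1, and stage 2 waits for outcomes that can no longer cause a futility stop

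*Combined protocol and SAP*

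**What the plan says.** Part 2 uses a Simon two-stage design. Six of the 16 stage 1 patients are carried over from Part 1. The futility rule in section 12.1 is: "If there are 7 or fewer responses in the first 16 patients enrolled, the study will be stopped". The same section defines the outcome broadly: "Withdrawal or progression prior to 24 weeks or missing 24-week assessment will be considered non-response". Section 12.3 does not replace Part 2 patients once they have begun treatment.

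To soften the expected halt in accrual, the Study Summary and sections 4.4, 12.1 and 12.4.1 allow three further patients "if no more than 5 of 16 patients have experienced treatment failure (i.e., the addition of secondary systemic therapy or disease relapse or death", assessed at the end of week 12.

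Section 4.4 places the interim analysis after all 16 have either met the failure criteria or completed six months of combination therapy. Stage 2 opens only as a result of that analysis. No section closes the three-patient allowance when stage 1 is already lost, and none opens stage 2 once the futility stop has been ruled out.

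**The concern.** The early-enrolment rule and the stage 1 decision look at different events. Withdrawal, and GVHD progression without a listed event, count against stage 1 but not in the rule. Up to three patients could therefore start the regimen after the futility stop has become certain. In the other direction, accrual to a regimen that has already cleared stage 1 waits for outcomes that cannot change the decision.

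**Working it through.** **Plan's own figures.** Inputs from section 12.1: response rates 0.40 (null) and 0.60 (alternative), one-sided test, stop at 7 or fewer of 16, and "The null hypothesis will be rejected if 24 or more responses are observed in 46 patients".

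P(reject) = sum over x = 8 to 16 of P(Bin(16, p) = x) × P(Bin(30, p) ≥ 24 − x)

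- p = 0.40: 0.0486
- p = 0.60: 0.8006

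This agrees with the stated result: "This design yields a type I error rate of 0.0486 and a power of 80" per cent. P(stop at stage 1) is 0.716 at p = 0.40 and 0.142 at p = 0.60.

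**When stage 1 is settled.** It is lost at 16 − 7 = 9 non-responders and passed at 8 week-24 responses. Example: five listed failures plus four withdrawals by week 12 give 5 + 4 = 9 non-responders, so at most 7 responses remain possible. The listed count is 5, so the early-enrolment rule is still met.

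**How often the rule is met with stage 1 already lost.** Let f be the probability of a listed failure by week 12, and w the probability of a certain non-response by week 12 for an unlisted reason. The documents give neither, so both are assumed.

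P = sum over F = 0 to 5 and W ≥ 9 − F of [16! / (F! W! (16 − F − W)!)] × f^F × w^W × (1 − f − w)^(16 − F − W)

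| f | w = 0.10 | w = 0.20 | w = 0.30 |
|---|---|---|---|
| 0.10 | 0.1% | 2.4% | 14.0% |
| 0.20 | 0.8% | 9.6% | 33.4% |
| 0.30 | 1.8% | 15.7% | 40.2% |

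**How well the rule screens.** P(F ≤ 5) is 99.7%, 92% and 66% for f = 0.10, 0.20 and 0.30. At a 40% response rate, the chance that stage 1 fails given that the rule is met is 0.715, 0.695 and 0.610, against 0.716 with no rule. For f of 0.10 to 0.20 it says almost nothing about the stage 1 result.

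**How often stage 1 is settled early.**

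- p = 0.60: P(Bin(15, 0.60) ≥ 8) / P(Bin(16, 0.60) ≥ 8) = 0.787 / 0.858 = 0.917. So 92% of trials that pass have their eighth response before the sixteenth outcome, with the eighth response at outcome 12.5 on average.
- p = 0.40: P(Bin(15, 0.40) ≤ 6) / P(Bin(16, 0.40) ≤ 7) = 0.610 / 0.716 = 0.852. So 85% of trials that stop have their ninth non-response before the sixteenth outcome.

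**Time saved.** This was simulated at p = 0.60 in trials that pass stage 1. The six carried-over patients enter earlier, ten are accrued at an assumed rate, and outcome is known 24 weeks plus a one-week lead-in after entry. The allowance is assumed to open when the sixteenth patient reaches week 12.

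| Accrual per month | Idle months, plan with allowance used | Idle months, stage 2 opened at 8 responses | Difference |
|---|---|---|---|
| 1 | 3.5 | 2.6 | 0.9 |
| 2 | 4.3 | 4.0 | 0.3 |
| 3 | 4.8 | 4.6 | 0.2 |

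The third column includes no bridging patients. Keeping the allowance as well cannot lengthen the pause.

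**Effect on error rates.** Stopping at 9 non-responses or continuing at 8 responses gives the same decision as waiting for all 16, whatever the order of outcomes. Recursion through the curtailed design returns 0.0486 and 0.8006.

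**The case against.** Waiting for every stage 1 outcome is the ordinary form of a two-stage design, and curtailment is a refinement. The allowance is a declared and bounded compromise: three patients, with quarterly toxicity monitoring (section 11.3.2) and quarterly DSMC review (section 16.3). All of this stands, and it limits the harm without defending the mismatch.

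Four stronger readings are tempting but not supported.

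- **That the defect occurs in most failing trials.** At a 40% response rate and f = 0.20, the rule is met and stage 1 later stops in 64% of trials. In most of these the result is still open at week 12, because a patient with unchanged disease or a mixed response may yet respond by week 24. A stop at nine confirmed non-responders would not have barred entry there. The table of already-lost probabilities is the relevant measure.
- **That months of pause would be saved.** Comparing with the last patient's full period of about 5.75 months (25 weeks) ignores the three-patient allowance that the plan already contains.
- **That the rule gives no protection.** It is strict on the severe events that it lists. Replacing it with one count closed at nine non-responses of any kind would admit patients after six, seven or eight listed failures, which the present limit blocks. At w = 0.10, enrolment would be allowed in 86% of trials instead of 66% (f = 0.30), or 97% instead of 92% (f = 0.20).
- **That eight responses make stopping impossible.** They exclude only the futility stop. The toxicity rule and the DSMC can still stop the trial, and the responses must be at week 24, since an earlier one can be lost.

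A further objection also stands: a certain non-response is not yet cleanly defined. Section 12.1 does not say whether withdrawal means from treatment or from study, and the example of four withdrawals depends on this if those patients stay in follow-up. Section 12.1 counts progression as non-response and section 9.3 ends study therapy at progression. Section 4.1 allows limited prednisone for progressing GVHD without counting it as failure of the primary endpoint, and section 6.7.1 adds prednisone-based failures that the early-enrolment list does not mention.

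**Conclusion.** The point holds, with limited consequences. The early-enrolment rule can be met after stage 1 is lost, and stage 2 can be held shut after the futility stop has been excluded. With 20% listed failures, the first has probability 0.8% to 33% as unlisted certain non-response by week 12 runs from 10% to 30%. It is rare if that share is about 10% or less, and at most three patients are affected. The second arises in 92% of trials that pass stage 1 at a 60% response rate, but the gain over the plan with its allowance in use is only about 0.2 to 0.9 months. The failure, non-response and accrual rates are assumptions. The counts of nine and eight follow directly from the plan. The validity of the test is not in question.

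**What to change.** Amend the Study Summary and sections 4.4, 12.1 and 12.4.1 together:

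1. Keep the limit of five listed failures at week 12. Add that no further patient is enrolled, and the futility stop is declared, once nine of the first 16 are confirmed non-responders under section 12.1.
2. Open stage 2 once eight of the first 16 have a confirmed CR or PR at Cycle 7 Day 1, with the toxicity rule and DSMC review still in force.
3. State whether withdrawal in section 12.1 is from treatment or from study, and reconcile the progression and prednisone wording of sections 4.1, 6.7.1, 9.3 and 12.1, so that a confirmed non-responder is unambiguous.
4. Clarify when the accrual hold begins. Section 12.1 places it after the 16 have completed 24 weeks, yet also describes a pause while they are being followed.

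The cost is wording and a running tally of confirmed week-24 outcomes for the DSMC. The small downside is that review is triggered by events instead of by calendar. Type I error (0.0486), power (0.80) and sample size stay as they are.

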#### **4.5 Number of Patients**

A total of 6 to 18 patients may be evaluated in Part 1 depending on the frequency of DLTs and the need for dose reductions. Upon dose confirmation, Part 2 will enroll 40 patients.

#### **4.6 Number of Study Centers**

This is a multisite study to be conducted at the Huntsman Cancer Institute at the University of Utah, Salt Lake City, Utah. Up to 3 additional sites may be included

#### **4.7 Study Duration**

The estimated duration of Part 1 is 6 to 18 months. The total duration of the study will be up to 3 years.

## 5 ELIGIBILITY CRITERIA

This eligibility checklist is used to determine patient eligibility and filed with the enrolling investigator's signature in the patient research chart.

Patient No. \_\_\_\_\_

Patient's Initials: (L,F,M) \_\_\_\_\_

### 5.1 Inclusion Criteria

**Yes/No (Response of "no" = patient ineligible)**

- 5.1.1 \_\_\_\_\_ Male or female subject aged  $\geq 18$  years.
- 5.1.2 \_\_\_\_\_ Active, clinically diagnosed, moderate or severe chronic GVHD as defined by the NIH Consensus Development Project Criteria (See Appendix 2).
- 5.1.3 \_\_\_\_\_ History of an allogeneic hematopoietic cell transplant with any conditioning regimen, donor, or graft source.
- 5.1.4 \_\_\_\_\_ Need for systemic treatment for chronic GVHD as assessed by the treating investigator.
- 5.1.5 \_\_\_\_\_ No previous systemic treatment for chronic GVHD.
- Note: Participants may be receiving immunosuppressants for the prophylaxis or treatment of acute GVHD, but these medications must have been stable for at least 2 weeks prior to the initiation of study therapy. Prednisone dose (or its equivalent) should be at doses of  $\leq 0.25$  mg/kg/d for at least 2 weeks prior to the initiation of study therapy.
- Topical or inhaled treatments for chronic GVHD are allowed. Any prior ECP treatments for the management of acute GVHD must have occurred  $> 4$  weeks prior to the initiation of itacitinib treatment.
- 5.1.6 \_\_\_\_\_ Able to swallow and retain oral medication.
- 5.1.7 \_\_\_\_\_ Life expectancy  $> 24$  weeks.
- 5.1.8 \_\_\_\_\_ Karnofsky performance status  $\geq 60$
- 5.1.9 \_\_\_\_\_ Evidence of myeloid and platelet engraftment:
- Absolute neutrophil count  $\geq 1000/\text{mcL}$
  - Platelet count  $\geq 25,000/\text{mcL}$

Note: Use of growth factors and transfusion support is allowed during the study; however, growth factors and transfusion support to reach a minimum ANC or

platelet count for inclusion are not allowed within the 7 days before the screening laboratory assessment.

**5.1.10** \_\_\_\_\_ Adequate organ function as defined as:

- **Hepatic:**
  - Total bilirubin  $\leq 2$  mg/dL
  - AST(SGOT)/ALT(SGPT)  $\leq 2.5 \times$  institutional ULN (unless of non-hepatic origin). AST/ALT  $\leq 5 \times$  ULN is acceptable if associated with chronic GVHD.
- **Renal:**
  - eGFR  $\geq 30$  mL/min/1.73 m^2 as calculated using the Modification of Diet in Renal Disease formula or by the Cockcroft-Gault formula:
    - Males:  $\frac{(140 - \text{age}) \times \text{weight}[\text{kg}]}{\text{serum creatinine} \left[ \frac{\text{mg}}{\text{dL}} \right] \times 72}$
    - Females:  $\left( \frac{(140 - \text{age}) \times \text{weight}[\text{kg}]}{\text{serum creatinine} \left[ \frac{\text{mg}}{\text{dL}} \right] \times 72} \right) \times 0.85$
- **Coagulation:**
  - PT/INR  $< 1.5 \times$  ULN and PTT (aPTT)  $< 1.5 \times$  ULN (unless abnormalities are unrelated to coagulopathy or bleeding disorder). When treated with warfarin or other vitamin K antagonist, then INR  $\leq 3 \times$  ULN.

**5.1.11** \_\_\_\_\_ Willingness to avoid pregnancy or father children based on the criteria below and as described in Section 5.4.2:

- Woman of nonchildbearing potential (i.e., surgically sterile with a hysterectomy and/or bilateral oophorectomy for at least 3 months OR  $\geq 12$  months of amenorrhea and at least 50 years of age).
- Woman of childbearing potential who has a negative serum pregnancy test at screening and negative urinary test before the first dose on Day 1 and who agrees to take appropriate precautions to avoid pregnancy (with at least 99% certainty) from screening through safety follow-up. Permitted methods that are at least 99% effective in preventing pregnancy should be communicated to the subject and their understanding confirmed.
- Men who agree to take appropriate precautions to avoid fathering children (with at least 99% certainty) from screening through safety follow-up. Permitted methods that are at least 99% effective in

preventing pregnancy should be communicated to the subject and their understanding confirmed.

- 5.1.12 \_\_\_\_\_ Able to provide informed consent and willing to sign an approved consent form that conforms to federal and institutional guidelines.

## 5.2 Exclusion Criteria

### Yes/No (Response of “yes” = patient ineligible)

- 5.2.1 \_\_\_\_\_ Subjects with score 3 lung GVHD or biopsy-proven bronchiolitis obliterans.
- 5.2.2 \_\_\_\_\_ Participants have uncontrolled manifestations of acute GVHD.
- 5.2.3 \_\_\_\_\_ Treatment with any investigational medication within  $\leq 30$  days or 5 half-lives, whichever is longer, before the first dose of study drug.
- 5.2.4 \_\_\_\_\_ Patients who have received any previous systemic treatment for chronic GVHD, including corticosteroids, prior to Cycle 1, Day 1.
- Note: Prior and concomitant use of Calcineurin-Inhibitors (CNIs) for prevention and treatment of acute GVHD, as well as topical/inhaled steroids, is acceptable.
- 5.2.5 \_\_\_\_\_ Received prior JAK inhibitor therapy for any indication  $\leq 4$  weeks prior to Cycle 1 Day 1.
- 5.2.6 \_\_\_\_\_ Patients with relapsed or progressive malignant disease or any post-transplant lymphoproliferative disease.
- 5.2.7 \_\_\_\_\_ Chronic GVHD occurring after a non-scheduled donor lymphocyte infusion (DLI) administered for pre-emptive treatment of malignancy recurrence. Participants who have received a scheduled DLI as part of their transplant procedure and not for management of malignancy relapse are eligible.
- 5.2.8 \_\_\_\_\_ Inability to swallow food or any condition of the upper gastrointestinal tract that precludes the administration of oral medications.
- 5.2.9 \_\_\_\_\_ Any contraindication for extracorporeal photopheresis (ECP) per the treating investigator’s discretion.
- 5.2.10 \_\_\_\_\_ Subject has a concurrent illness which in the opinion of the investigator may interfere with the treatment and evaluation of the subject.
- 5.2.11 \_\_\_\_\_ Pregnant or currently breast-feeding.

Note: INCB039110 is a JAK1 inhibitor with the potential for serious or life-threatening birth defects or abortifacient effects. Because there is an unknown but potential risk for adverse events in nursing infants secondary to treatment of

the mother with INCB039110, breastfeeding should be discontinued if the mother is treated with INCB039110. These potential risks may also apply to other agents used in this study.

- 5.2.12** \_\_\_\_\_ Vaccinated with live, attenuated vaccines within 4 weeks of the first dose of study drug and while on trial.
- 5.2.13** \_\_\_\_\_ Use of any prohibited concomitant medications as described in Section 6.5. A washout period of prohibited medications for a period of at least 5 half-lives or as clinically indicated should occur prior to the start of treatment.
- 5.2.14** \_\_\_\_\_ Inadequate recovery from toxicity and/or complications from major surgery before starting therapy.
- 5.2.15** \_\_\_\_\_ Unwillingness to be transfused with blood components during the study.
- 5.2.16** \_\_\_\_\_ History of other malignancy (not including the underlying malignancy that was the indication for the transplant), with the following exceptions:
- Malignancy treated with curative intent and with no evidence of active disease present for more than 3 years prior to Screening and felt to be at low risk for recurrence by the treating physician.
  - Adequately treated non-melanomatous skin cancer or lentigo maligna melanoma without current evidence of disease.
  - Adequately treated cervical carcinoma in situ without current evidence of disease.
- 5.2.17** \_\_\_\_\_ The subject has uncontrolled, significant intercurrent or recent illness including, but not limited to, the following conditions:
- Clinically significant or uncontrolled cardiac disease, including unstable angina, acute myocardial infarction within 6 months of enrollment, NYHA Class III or IV congestive heart failure, circulatory collapse requiring vasopressor or inotropic support, or an arrhythmia that requires therapy.
  - A clinically significant respiratory disease that requires mechanical ventilation support or  $\geq 50\%$  oxygen.
  - Any uncontrolled active systemic infection or active infection requiring systemic treatment that was ongoing  $\leq 7$  days before screening. Subjects with acute infections requiring treatment should delay screening/enrollment until the course of therapy has been completed and the event is considered resolved. Prophylactic antibiotics will be permitted.
  - Cholestatic disorders, or unresolved sinusoidal obstructive syndrome/veno-occlusive disease of the liver (defined as persistent total bilirubin

> 2 mg/dL, or abnormalities not attributable to GVHD and ongoing organ dysfunction).

- 5.2.18 \_\_\_\_\_ History of thromboembolic event within 1 month before study registration.
- 5.2.19 \_\_\_\_\_ HIV-infected patients on effective antiretroviral therapy with an undetectable viral load within 6 months are eligible for this trial.
- 5.2.20 \_\_\_\_\_ Active HBV or HCV infection that requires treatment, or at risk for HBV reactivation (i.e., positive HBsAg). Participants with negative HBsAg and positive total HbC antibody may be included if HBV DNA is undetectable at the time of screening. Participants who are positive for HCV antibodies are eligible only if PCR is negative for HCV RNA. Participants whose immune status is unknown or uncertain must have results confirming immune status before enrollment. Serology results performed less than or equal to 6 months prior to the first planned dose of itacitinib are acceptable for determining eligibility.
- 5.2.21 \_\_\_\_\_ Known prior severe hypersensitivity to investigational product or any component in its formulations, including known severe hypersensitivity reactions to monoclonal antibodies (NCI CTCAE v5.0 Grade  $\geq$  3).
- 5.2.22 \_\_\_\_\_ Any condition that would, in the investigator's judgment, interfere with full participation in the study, including administration of study drug/treatment and attending required study visits; pose a significant risk to the participant; or interfere with the interpretation of study data.
- 5.2.23 \_\_\_\_\_ Unable to understand the purpose and risks of the study and to provide a signed and dated informed consent form (ICF) and authorization to use protected health information (in accordance with national and local subject privacy regulations) per the investigator's assessment.

**Time**

### **5.3 Recruitment Strategies**

Potential patients will be identified by Investigators in the setting of their outpatient clinics.

### **5.4 Lifestyle Considerations**

#### **5.4.1 Meals and Dietary Restrictions**

Participants should be instructed to refrain from the consumption of pomegranates, pomegranate juice, grapefruits, grapefruit juice, or Seville oranges as these are known to inhibit cytochrome CYP3A4 enzymes and may increase exposure to itacitinib.

